Ethics Committee as this is not a comparative interventional trial. The three independent committee members will review safety, recruitment and ethical data, and would be able to close the trial.

We will use a risk adapted approach to monitoring. Recruitment and progress against milestones will be monitored by the study team at monthly Trial Management Meetings. A quality assurance programme will ensure consistent and high quality approaches to consent and implementation of the clinical rule. We will define an adverse event as one that occurs directly as a result of the clinical prediction tool (patient report of substantial worsening of pain and/or symptoms within 2 days of the test) and serious adverse events as any hospitalisation or death that occurs within 2 days of the test, and would not have been anticipated as part of clinical management at initial presentation.

Inclusion of people from ethnic minorities

Our sampling frame of EDs include a number of departments that have catchments with substantial ethnic minority communities (in particular Birmingham Heartlands). In the HTA funded Managing Injuries of the Neck Trial, we translated materials into a range of languages but found no evidence that the translated materials were used in preference to an English language version. We will explore the need to translate materials at each site, as well as the range of languages and take appropriate action. Translation services are available in NHS Trusts.

3. Research Governance

The research will be sponsored by the University of Oxford (with appropriate insurance policies in place) and follow Oxford Clinical Trial Research Units Standard Operating Procedures. This study will be fully compliant with the research governance framework and MRC Good Clinical Practice guidelines.

4. Study Management

This study will require careful management with stages 1 and 2 feeding vital information into stage 3. The Principal Investigator will be [name]. Day-to-day management will be undertaken by [name] and an experienced Study Co-ordinator. Study management group meetings will be held on a monthly basis to monitor progress and obtain input from the appropriate co-applicants and site investigators at the relevant stages of the study. In addition, 6-monthly co-applicant meetings will be held to ensure close involvement from all parties.

5. Project Timetables and Milestones

We propose an ambitious two and a half year study beginning in November 2014 (Table 2). We will begin governance and approval processes in the pre-funding stage. We will analyse the CAST data set and systematically review the literature concurrently over the first 3 months. Immediately following this we will conduct the expert and PPI consensus process in order that the initial tool is finalised ready for validation at the end of month 6. We will have approvals in place to commence recruitment in month 7 with the 5 site initiations staggered over 2 months. Follow-up of participants will continue until month 25. Data cleaning, analysis and final reporting will be carried out over the last 6 months of the project.

Table 2 – Project timetable

Quarter	1	2	3	4	5	6	7	8	9	10
Stage 1										
Analysis of CAST data set										
Stage 2										
Systematic Review										
Expert and PPI consultation										
Prognostic tool finalised for validation										
Stage 3										
Ethical and governance approvals										
Site training and set up										
Recruitment for ED cohort study										
Follow-up for ED cohort study										
Data entry and cleaning										
Analysis, reporting and dissemination										

6. Research Team

[name] will be Principal Investigator. She is a physiotherapist and a fellow of the Royal Statistical Society. She has been CI on NIHR HTA-funded studies that span primary, secondary and tertiary care, including trials in NHS EDs.

[name] will lead the statistical input. He is currently the Principal Investigator of an MRC methodology grant to develop statistical methods and reporting guidelines for prognostic studies. [name] will be responsible for the day to day management of the study. He previously co-ordinated the HTA funded Managing Injuries of the Neck Trial which recruited over 3000 patients through EDs in 18 months. He contributed to recruitment in the HTA funded CAST trial.

[name] will provide ED clinical and research expertise and act as local PI for recruitment in the validation cohort study. He has been PI and co-applicant on numerous NIHR HTA-funded studies in EDs including RATPAC (n=2243) and 3Mg (n=1109) trials.

[name] will also provide ED clinical and research expertise and act as local PI for recruitment in the validation cohort study at Heart of England Foundation Trust. He was previously National Clinical Director for Urgent and Emergency Care.

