Assessment of the injury in the hyper acute phase is challenging, the ankle is often so swollen and painful that it cannot easily be touched. Most patients are advised to rest, elevate, apply ice and compression, and are often issued with crutches. Use of X-ray has been effectively controlled through the Ottawa guidance,⁶ with only the most concerning injuries being X-rayed (or equivalent) to exclude fracture. Where clinicians are concerned about the degree of injury, most providers operate a system of review within one week in a trauma or equivalent injury service. This time frame allows dissolution of some swelling, and greater certainty in ascertainment of injury severity and presence of other significant mechanical derangement.⁷ Treatment options at this stage include further watchful waiting, diagnostics, intensive physiotherapy or immobilisation. Surgery may be considered at this stage, although most centres would initiate a test of conservative treatment first. We have previously published a survey of practice, which whilst quite an old publication remains an accurate reflection of the current management.⁸

Value of a prognostic tool

A prognostic tool is indicated to identify patients likely to experience poor outcome. There are effective treatments available, and it is generally accepted that early intervention is preferable. There are clearly several steps where better prognostic information could yield benefit to the NHS and to patients as follows; [1] Increase the certainty that an early review is merited, and avoid unnecessary appointments [2] Better target treatments and diagnostics, earlier in the recovery pathway [3] Be re-assured that patients not followed up are on a positive recovery trajectory. Volume is a key issue for sprains. Cost savings will accrue if treatments are more efficiently targeted.

Any prognostic tool needs to be simple to complete in the ED. Ideally a tool which requires a once only administration is preferable, although there are several possibilities which we can explore in the CAST data set. The issues that we will explore during development will be variable selection, timing and method (self-report versus clinical examination).

Requirements of a prognostic tool

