There are several methods that we could use to gain consensus or information on preferences (including Delphi methods, Discrete Choice Experiments, and face to face methods).³⁸ We have opted for a method (modified nominal group technique (MNGT)) which is well recognised, can be operationalised with relative ease, has a solid audit trail, and is based on face to face consensus building. We have previously used this technique to build consensus on injury outcome measures.

The MNGT is centred around three phases. First is the preparation of briefing papers. For these we will use the systematic review detailed in the preceding section (or short report of), a lay report of the modelling elements completed in Stage 1, and a number of alternative template presentations for the prognostic tool. Additional predictive factors where there is consistent evidence of moderate or high risk will be considered by the participants of the MNG to decide if the factors are sufficiently distinctive or potentially simpler alternatives to existing elements of the prognostic tool derived from the development dataset. The MNG will evaluate and advise on the practicalities of extra measures. The consensus element is achieved by small groups, with independent facilitation, and a pre-specified set of questions. Consensus is achieved in two stages. The first round is identification of issues, and general discussion. The second round is resolution and consensus. We will use experienced and independent facilitators and ensure all opinions are heard and considered. There is no formal estimation of the degree of consensus and we will not set a formal rule in relation to this. The face to face discussions will be invaluable in decision making.

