The participants will be a maximum of 12 clinicians (including ED doctors, trauma/sports physicians, physiotherapists, ED nurses, and minor injury unit staff), and 12 patients (representing a range of age, gender and physical activity/sport participation). The tool will then undergo final revision and common sense testing before release for external validation. Our plan will be to present two schedules of data collection for completion (excluding data on sample characteristics that are not contained in either schedule). The first will be prognostic tool as generated by the development data set. These will require a degree of formatting to convert data collected in a clinical research form, to an easy to complete prognostic tool. The additional predictive factors will also be formatted in a similar and completely complementary manner, but collected on the separate schedule (and after completion of the primary tool). The two schedules will be collected by the same clinician. In this way if any of the additional factors is confirmed as important, we will add them into the final tool, causing least disruption to the process of validation. If there is more than one additional predictive factor, we will randomise the order of data presentation across participants to gain insight into whether the order or opportunity to provide additional data in anyway biases the sample.

All participants of the consensus exercise will provide consent to participate. PPI members will be paid for their time and contribution, clinicians will not.

Stage 3: Externally validate and optimise the tool in a new cohort of patients recruited from NHS Emergency Departments

We will externally validate the prognostic tool developed in stages 1 and 2 in a new prospective cohort. We will recruit 675 people from 5 EDs, from a pool of 7,500 to 10,000 ankle sprains per annum at a conservative rate of 15 sprains per centre per month. We have provisional agreement from an additional 5 EDs to participate if required.

We cannot be completely certain of how this element of the study will run, as this will vary depending on the final tool. We have at this stage assumed that the tool will require contact at initial attendance and one early follow up visit (at around 5 days), and will include a mix of self-report and clinical tests. We have considered a range of other possibilities, and can provide these if needed.

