Analysis: The performance of the tool will be assessed using calibration and discrimination metrics. Calibration will be assessed graphically with results for patients grouped by similar probabilities (tenths) and compare the mean predicted probability to the mean observed outcome.^{23,24} The calibration plot will also be supplemented with estimates of the calibration slope and intercept. The discrimination of various prognostic models will be summarised with the concordance index (equivalent to the Area Under Receiver Operating Characteristic curve) with 95% confidence interval. Additional predictors not contained in the development dataset will be examined to see whether they improve the performance of the prognostic model using net reclassification improvement (NRI) and integrated discrimination improvement (IDI).⁴¹

Neither calibration nor discrimination captures the clinical usefulness of the prediction model (i.e. how does using the prediction model improve on a default policy of no prediction model). This will be examined using decision curve analysis, a relatively novel yet increasingly recommended approach in evaluating the predictive performance of a prediction model. It calculates the net benefit of using the model compared to not using the model,³² evaluating and determining ranges of cut-off values for decision-making. The approach permits evaluation of the tools over a range of thresholds and the model with the greatest net benefit (i.e. the number of true positives penalised by a weighted proportion of the false-positives) will be considered as the preferred prediction model. The results will be converted into 'an additional x patients per 1000' who would be identified using the prediction tool compared to not using the tool. If additional predictors are found to be helpful, we will evaluate the incremental value of the predictors and update the model to accommodate these accordingly.^{23,31} A model with the greatest net benefit (i.e. the number of true positives penalised by a weighted proportion of the false-positives) will be considered as the preferred prediction model.³²

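### A new factor may be nominated as a simpler alternative to a tool item, but Stage 3 judges every new factor by added value only, and its only stated action is to add it

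*Protocol*

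**What the plan says.** All references are to the Protocol.

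- **Stage 2b (Expert consensus process), nomination.** The consensus group considers factors with consistent evidence of moderate or high risk and decides whether they are "sufficiently distinctive or potentially simpler alternatives to existing elements of the prognostic tool derived from the development dataset". The first ground concerns new information. The second concerns standing in for something already in the tool.
- **Stage 2b, data collection.** Two schedules are planned. "The first will be prognostic tool as generated by the development data set". New factors go on a second form, completed afterwards by the same clinician. The stated consequence is: "if any of the additional factors is confirmed as important, we will add them into the final tool".
- **Stage 3, Analysis.** "Additional predictors not contained in the development dataset will be examined to see whether they improve the performance of the prognostic model", using NRI and IDI. If they are found helpful, "we will evaluate the incremental value of the predictors and update the model to accommodate these accordingly". The preferred model is "the model with the greatest net benefit".
- **Value of a prognostic tool.** "Any prognostic tool needs to be simple to complete in the ED".

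**The concern.** The two grounds for nomination ask different questions. For a distinctive factor the question is whether it tells us something the tool does not, and an added-value test answers that. For a simpler alternative the question is whether the tool would do as well with this item in place of the harder one. An added-value test does not answer that, because the harder item stays in the model throughout.

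The better the alternative mirrors the item it would replace, the less it can add beside it. An ideal substitute is therefore the factor most likely to be reported as unhelpful. If it does pass, the stated action puts it next to the item it was meant to displace, and the tool becomes longer. Neither result tells the consensus group whether the simpler measure can be used.

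**Working it through.** **1. The plan's own figures.** From the Sampling paragraph of Stage 3:

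- 100/0.32 = 312.5, so 313; 100/0.26 = 384.6, so 385. Both agree with the stated range.
- 100/0.20 = 500; 500/(1 − 0.25) = 666.7, so 667, against a stated 675. This agrees within rounding.
- Analysed: 675 × 0.75 = 506. Events: 506 × 0.20 = about 101.

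The sample size reproduces and is not in question.

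**2. The rules side by side.**

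| Ground for nomination | Question it raises | Test stated | Action stated |
|---|---|---|---|
| Distinctive | Does it add information? | Improvement over existing model | Add |
| Simpler alternative | Can it replace item X? | Improvement over existing model | Add |

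The test and action do not fit the second row.

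**3. Size, by simulation.** The protocol gives no effect sizes, correlations or acceptance criterion, so those used here are assumptions. The rest of the tool (R) and a construct (C) each have log-odds 0.7 per SD, with the intercept set to give 20% events. The existing item A and the new item B are equally good measures of C: A = √ρ·C + √(1−ρ)·e₁ and B = √ρ·C + √(1−ρ)·e₂, so corr(A,B) = ρ. Samples are of 506.

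| ρ | c, original (R+A) | c, both (R+A+B) | c, swapped (R+B) | B passes LR 5% | B passes IDI z>1.96 | B passes p<0.2 |
|---|---|---|---|---|---|---|
| 0.7 | 0.723 | 0.731 | 0.723 | 57% | 45% | 83% |
| 0.8 | 0.732 | 0.737 | 0.731 | 41% | 29% | 64% |
| 0.9 | 0.737 | 0.740 | 0.737 | 25% | 18% | 51% |

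Swapping changes c by less than 0.001. Adding raises it by 0.008, 0.005 and 0.003. Repeat runs of the 5% test gave 53 to 57%, 41 to 42% and 24 to 26%. The p<0.2 column borrows the Stage 1 backward-selection threshold by analogy; the protocol does not apply it to Stage 3.

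**4. Sensitivity to the strength of the construct** (5% likelihood-ratio test; R kept at 0.7):

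| Log-odds of C | ρ=0.5 | ρ=0.7 | ρ=0.8 | ρ=0.9 |
|---|---|---|---|---|
| 0.4 | 29% | 22% | 20% | 12% |
| 0.6 | 53% | 46% | 33% | 19% |
| 0.8 | 77% | 65% | 47% | 30% |

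Close substitutes (ρ of 0.8 or more) fail more often than they pass at a 5% criterion. Looser substitutes for a strong construct are more often added.

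**5. What a swap comparison could show.** The SD of c(swapped) − c(original) was 0.0161, 0.0129 and 0.0102 at ρ = 0.7, 0.8 and 0.9. Multiplying by 1.96 gives 95% intervals of about ±0.032, ±0.025 and ±0.020. For a truly equal item and a tolerated loss m, the chance of acceptance is:

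- lower 95% limit must clear −m: Φ(m/SD − 1.96). For m = 0.02 this is 24%, 34%, 50%; for m = 0.01 it is 9%, 12%, 16%. Direct simulation gave 26/33/52% and 9/11/16%.
- estimated difference must clear −m: Φ(m/SD). For m = 0.01 this is 73%, 78%, 84%. Simulation gave 74 to 84%.

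An interval-based rule would therefore reject an equally good item in about half to nine-tenths of studies, no better than the present rule.

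**The case against.** The strongest reply is that the choice of candidate models belongs in the SAP, that nothing in the protocol forbids a swap, and that both schedules are completed on the same participants, so a swapped model can be fitted at any time. The Analysis paragraph speaks of several models and of updating. This stands in part: the design does not block the comparison. But the protocol does more than leave detail open. It fixes the test (improvement) and the action (add). The updating clause is reached only once a factor has been found helpful, which an equal substitute need not be. A greatest-net-benefit rule gives no credit for equal performance with less burden. The revision step before release does not help either: the first schedule stays as the development data produced it, and a factor absent from CAST has no weight there.

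A second reply is that simplicity is handled elsewhere. Stage 1 compares self-report with clinical examination models, and the consensus group weighs accuracy against inconvenience. That is true, but Stage 1 can only compare items that CAST holds.

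A third is that the case may never arise. Stage 2 expects little departure from the CAST variables. In Appendix 1 the only item outside CAST that clearly duplicates a CAST item is clinician-rated range of motion, which is not obviously simpler than the self-reported version. This limits the point. Stage 2 does, however, note that alternative physical tests exist and that additional variables cannot be ruled out.

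A reader might infer that good simpler items would mostly be discarded. The document does not support that: it names NRI and IDI without a cut-off, and at p<0.2 the alternative passes in about half or more of studies.

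**Conclusion.** The mismatch is in the text and does not depend on the simulation: replacement is one of two grounds for nomination, yet the only test is added value and the only action is addition. An equally good simpler item is either rejected or placed beside the item it should replace.

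How often each occurs cannot be fixed from the protocol. Under the stated assumptions a 5% test accepts the item in about 25 to 57% of studies at correlations 0.9 to 0.7, and p<0.2 in about 51 to 83%. Rejection is the usual result only for close substitutes judged at a 5%-type criterion.

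It would also be wrong to infer that the external validation is compromised. Validation of the original tool and the target of 675 are unaffected. What is at stake is the content and length of the final tool, and only if an alternative is nominated. The wording should still be changed, before Stage 3 results are seen.

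**What to change.** 1. **Label before Stage 3.** Have the consensus group record each nominated factor as *additional* or as *alternative to item X*, naming the item.
2. **Amend Stage 2b and the Stage 3 Analysis paragraph** so that only *additional* factors are judged by NRI, IDI and incremental value and then added.
3. **For an alternative,** fit the tool with item X replaced. Compare it with the original tool with item X's weight re-estimated in the same way, so that the swap is not favoured, and correct both for optimism by bootstrap. Report the paired difference in c-index and net benefit with 95% intervals, plus calibration. Do not keep both items merely because the alternative shows incremental value.
4. **Decision.** Base replacement on the estimated difference against a loss agreed beforehand, and report the interval as the precision. Do not require the lower 95% limit to clear a margin of 0.01 to 0.02 in c, for the reason shown in step 5 of the working.

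**Cost.** Protocol wording, one label and one tolerated loss per alternative, and one extra model on data already planned. No extra patients or visits are needed. The replacement weight would be estimated in Stage 3 and have only internal (bootstrap) validation. A rule based on the estimate would also accept an item whose true loss equals the tolerance about half the time (Φ(0) = 0.5), so the interval must be shown beside the decision.

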Depending on the final format, the patient or ED clinicians (or both) will be asked to complete the prognostic tool. Although the predictor variables may be evident as per usual clinical practice, the prognosis will not be computed until final 9 month follow up is complete for each participant. Clinicians will be asked to continue to manage patients within the normal pathways at each of their hospitals, and we will record resource use. We may ask participants to return to the site, or complete some self-tests at home if further examination is indicated.

The questionnaires collected from participants at 4 and 9 months and will include details of severe and persistent symptoms, instability (as previous discussed), the validated Foot and Ankle Outcome Score,³⁹ health service resource use during follow up, and health related quality of life. Participants will be able to choose to respond via the web or a postal questionnaire. Additional demographic information will be collected if this is not included in the prognostic tool (for example sprain severity, age, gender, employment status). We are unlikely to include imaging techniques as either a component of the prognostic tool, or during follow up, although we will record if an image is taken and used in the practice. There is no indication in the literature that imaging adds to prognostic information, although a study of low dose CT scanning is being completed by one of the co-applicants of the study.

Sampling: The same principles apply to the sample size calculation stated here, as in Stage 1 justification for modelling. Current recommendations are that a minimum of 100 outcome events are required for external validation.^{24,40} We anticipate the event rate to be between 26% and 32%, this would require an overall sample size of between 313 and 385. Assuming a 25% loss to follow-up and a lower event rate (20%) when recruiting all grades of ankles sprains we will target 675 patients to ensure the event rate is achieved.

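### The calibration plot by tenths rests on about 10 events per point; a smoothed curve with a 95% band on the same data would show the shape of miscalibration better

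*Protocol*

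**What the plan says.** The Analysis paragraph under Stage 3 of the protocol describes a calibration plot with patients "grouped by similar probabilities (tenths) and compare the mean predicted probability to the mean observed outcome". The next sentence adds two summary estimates: "The calibration plot will also be supplemented with estimates of the calibration slope and intercept". The concordance index and decision curve analysis are also planned. A smoothed calibration curve is neither mentioned nor excluded.

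The Sampling paragraph of the same stage sets the size of the cohort. It starts from an event count: "Current recommendations are that a minimum of 100 outcome events are required for external validation". It then gives the expected rates: "We anticipate the event rate to be between 26% and 32%, this would require an overall sample size of between 313 and 385". It ends with the planning case: "Assuming a 25% loss to follow-up and a lower event rate (20%) when recruiting all grades of ankles sprains we will target 675 patients".

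**The concern.** A grouped plot uses only the patients in a group to estimate the observed risk at that point. With a cohort sized for about 100 events, ten groups leave few events in each, and fewest where predicted risk is low. The points will scatter even if the model is well calibrated, and where they fall depends on the cut-points.

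Slope and intercept use every patient and need no grouping. They show whether predictions are too high or too low overall, and whether they are too extreme or too narrow. They cannot show a departure that bends, such as predictions that are right in the middle and wrong at one end. Only the plot can show that.

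The low end matters for this tool. The section on the value of a prognostic tool lists, among its benefits, reassurance that patients who are not followed up are recovering well. The development trial left out minor sprains in people who could bear weight at day 3 to 5, whereas the validation cohort takes all grades. The tool will therefore be applied to patients of a kind that it was not built on. If calibration at low predicted risk cannot be read from the plot, over- or under-prediction there could go unnoticed.

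**Working it through.** **Inputs.** From the Sampling paragraph: at least 100 events, anticipated event rate 26% to 32%, planning rate 20%, loss 25%, target 675. From the Analysis paragraph: ten groups. The spread of predicted risk is not given, because the model has yet to be built. It is assumed here as a standard deviation (SD) of the linear predictor of 0.6 to 1.2.

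**The plan's own figures.** Sample size = events / event rate, then divided by (1 − loss).
- 100/0.32 = 312.5, so 313, and 100/0.26 = 384.6, so 385. Both match.
- 100/0.20 = 500, and 500/0.75 = 667, which agrees with 675 after slight rounding up.

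**Patients and events per tenth.**
- Followed up: 675 × 0.75 = 506. Per tenth: 506/10 = about 51.
- At 20%: 506 × 0.20 = 101 events, or 10.1 per tenth on average.
- At 26%: 132 events, or 13.2 per tenth. At 32%: 162 events, or 16.2 per tenth.

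**Precision of one point.** The Wilson 95% interval is [p + z²/2n ± z√(p(1−p)/n + z²/4n²)] / (1 + z²/n), with n = 51 and z = 1.96. For 10 events, p = 0.196, the centre is 0.217 and the half-width is 0.107.

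| Events out of 51 | Observed | 95% interval |
|---|---|---|
| 3 | 6% | 2% to 16% |
| 5 | 10% | 4% to 21% |
| 10 | 20% | 11% to 32% |
| 20 | 39% | 27% to 53% |

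**Events in the lowest tenth (simulated, 506 patients, 20% events, normal linear predictor).** With a well-calibrated model, the mean count is 3.9 at SD 0.6, 2.2 at SD 0.9 and 1.2 at SD 1.2. With SD 0.9 and a true calibration slope of 0.6 it is 4.3. Hence roughly 1 to 5. At SD 0.9 with good calibration, the highest tenth holds about 25.

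**Tenths against a smoothed curve.** The same simulation (600 replicates, lowess with span 0.75) compared each estimate of observed risk with the true risk in each tenth. At 20% events the root mean squared error was 0.050 to 0.054 for tenths and 0.027 to 0.031 for lowess. At 30% events (SD 0.9) it was 0.059 and 0.030. A separate simulation under the same range of SD gave 0.048 to 0.054 against 0.031 to 0.034. The gain also held in the lowest-risk fifth.

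**What slope and intercept already detect (SD 0.9, 20% events).** The table gives the power of a joint test of slope and intercept and of a chi-square test on the tenths.

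| True departure | Slope and intercept | Tenths |
|---|---|---|
| Uniform logit shift of −0.3 | 0.65 | 0.25 |
| Uniform logit shift of −0.5 | 0.99 | 0.82 |
| Curved (quadratic term 0.3) | 0.22 | 0.40 |

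The two summary numbers are stronger for a shift and weaker for curvature. Neither is strong for curvature.

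**The case against.** The strongest reply is that nothing in the protocol is wrong. It plans a recognised plot together with slope and intercept, makes no decision rest on the tenths, and does not rule out a smoother. Plotting detail usually belongs in a statistical analysis plan, which is not at hand. That stands as far as it goes: this is no error. But the grouped plot is a stated choice, not a gap, and a more precise display of the same data is available.

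A reader might infer that tenths cannot show miscalibration at all. The documents do not support that. Slope and intercept are planned and cover overall and proportional miscalibration. In the simulation the tenths alone detected a logit shift of −0.5 with power 0.82, and they did better than slope and intercept on a curved departure. Nor is coarseness the problem: the trouble is noise in each group and dependence on cut-points.

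A reader might also infer that curved miscalibration is the main risk in moving to all grades of sprain. The protocol does not say so. It expects a lower event rate (20%) and describes Grade I sprains as having a good prognosis, which points at least as much to an overall shift, and the intercept would detect that.

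Decision curve analysis over a range of cut-offs is planned as well, and it bears on whether low-risk patients can go without follow-up. It measures net benefit, however, and does not display agreement between predicted and observed risk.

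Finally, smoothing has a price. The curve depends on the span or the knots, stays uncertain where predictions are sparse, and adds no events at low risk. Its simulated advantage was found under assumed smooth truths.

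**Conclusion.** The point holds as a minor improvement. About 51 patients and an average of 10 events per plotted point follow directly from the protocol's planning figures. Ten is the conservative end; the anticipated event rates give 13 to 16. The planned plot is therefore an imprecise way to show the shape of miscalibration, which slope and intercept cannot supply, and it is weakest in the low-risk range that the tool is meant to serve.

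The counts in the lowest tenth, the error figures and the power figures depend on an assumed spread of predicted risk and on the simulated forms of departure. They are illustrative. The average counts and the Wilson intervals need no such assumption about spread. The sample size, the event count and the other planned measures are unaffected.

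**What to change.** In the Analysis paragraph of Stage 3, or in the statistical analysis plan, make a smoothed calibration curve the main display: loess, or a restricted cubic spline of the outcome on the linear predictor, with a 95% band. Keep the calibration slope and intercept as planned. Show the grouped points only as an overlay.

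Fix the span, or the number and position of the knots, before the outcome data are seen, and say that the curve is to be read with caution where predictions are sparse.

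The cost is a little more analysis work and the need to settle the smoother in advance. No further patients or data are needed, and the target stays at 675.
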